### 2. Objectives (include all primary and secondary objectives)

#### **Specific Aim 1: Identify patients who would benefit from early use of the OWSV.**

Hypothesis 1a: Several factors such as age, sex, educational level, primary diagnosis, indication for tracheostomy, co-morbidities, and severity of illness will significantly contribute to early tolerance of the OWSV.

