## 7. Study Statistics

- a. Primary outcome variable.

Speech intelligibility

- b. Secondary outcome variables.

- Patient characteristics
- Quality of Life
- Complications
- Time to events
- Length of stay
- Mortality

\*See codebook for list of additional variables

- c. Statistical plan including sample size justification and interim data analysis.

Mean, standard deviation, median and inter-quartile range will be calculated for continuous variables. Paired t-tests will be used to compare pre and post assessment scores for continuous variables. Frequencies and percentages will be calculated for categorical variables. Chi square and Fisher Exact tests will be used to compare pre and post assessment scores of categorical variables. Sample size is estimated based on 30% of tracheostomy patients who might be awake and interactive at the Johns Hopkins Hospital in 2016, as per the tracheostomy database. According to the 2014 data, we found that about 55 patients were awake and interactive while having a percutaneous tracheostomy tube at the hospital. Considering a 10% of the patients who may not be interested in the study, we will plan for a sample size of 50 with 25 in the intervention group and 25 in the control group.

- d. Early stopping rules.

If patients have changes in clinical condition that prevents cuff deflation, they will be dropped from the study. The study will be halted if any major complications occur from early trial of OWSV.

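### No analysis in section 7 relates the H1a patient factors to early valve tolerance, so Specific Aim 1 would get only descriptive summaries

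*Combined protocol and SAP*

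**What the plan says.** Section 2 heads Specific Aim 1 "Identify patients who would benefit from early use of the OWSV". Under it, Hypothesis 1a names "Several factors such as age, sex, educational level, primary diagnosis, indication for tracheostomy, co-morbidities, and severity of illness" and states that these "will significantly contribute to early tolerance of the OWSV". The factors are therefore the predictors and early tolerance is the outcome.

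Section 7a gives the primary outcome as "Speech intelligibility". Section 7b lists six secondary outcomes. The first is "Patient characteristics"; the others are quality of life, complications, time to events, length of stay and mortality. A footnote adds "See codebook for list of additional variables"; that codebook is not part of the document.

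Section 7c provides summary statistics for continuous variables, frequencies and percentages for categorical ones, and two test rules. Paired t-tests compare continuous scores between the two assessments. For the rest, "Chi square and Fisher Exact tests will be used to compare pre and post assessment scores of categorical variables".

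Tolerance appears in section 4a, item E.2.ii.1, as a duration recorded when the valve is trialled at Session 1 (12-24 hours after the procedure). Only the intervention group has that trial, and only if the speech-language pathologist finds the patient suitable. Section 8b says the trial may otherwise be deferred.

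**The concern.** The first aim of the trial needs an analysis with tolerance on one side and patient factors on the other. Section 7 gives tolerance no role by name, classes the factors as outcomes, and states tests that answer a different question: whether a score changed between sessions. A before-after change, even in a factor that can change such as organ-failure severity, does not show who tolerated the valve.

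At stake is whether Aim 1 gets a prespecified answer. Section 9a cites patient candidacy for early valve use as something the study may inform. Without a named outcome and a stated comparison, that question is either left to description or settled after the data are seen, by choosing among seven factors, several possible definitions of tolerance and several ways of handling patients who were not trialled.

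**Working it through.** **1. Hypothesis against plan**

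| Element | H1a (section 2) | Section 7 as printed |
|---|---|---|
| Outcome | early tolerance | not named in 7a or 7b |
| Predictors | 7 patient factors | patient characteristics listed as an outcome (7b) |
| Analysis | contribution of factors to tolerance | pre/post comparison of scores (7c) |

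The seven factors are age, sex, education, diagnosis, reason for tracheostomy, comorbidity and illness severity. Section 7c contains no regression, no correlation and no comparison of patients by tolerance. Chi-square or Fisher tests could relate a categorical factor to a binary tolerance variable, but 7c assigns them to the pre/post comparison. Factors with a stated analysis against tolerance: 0 of 7.

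**2. Patients who can contribute**

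The sample size in 7c is a feasibility count: about 55 patients less 10% not interested, 55 × 0.90 = 49.5, which reproduces the stated 50 (25 per arm). It involves no power calculation for any hypothesis. Controls have their first valve trial at Session 2 (48-60 hours), so early tolerance exists for at most 25 patients, fewer if trials are deferred.

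**3. What 25 patients can support**

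The two-sided 5% level, the even split and the tolerance rates below are assumptions; the plan gives none of them.

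- *Rank correlation with a continuous factor.* By the Fisher transformation, the 95% limits around zero are ±tanh(1.96/√(25 − 3)) = ±tanh(0.418) = ±0.395, or about ±0.40.
- *Difference between two equal categories (12.5 each).* The standard error in standard-deviation units is √(2/12.5) = 0.40. The 95% half-width is 1.96 × 0.40 = 0.78 SD. The difference detectable with 80% power is (1.96 + 0.84) × 0.40 = 1.12 SD.
- *One model with all seven factors, tolerance made binary.* Patients in the smaller class per predictor = min(t, 1 − t) × 25 / 7. For t = 50% this is 12.5/7 = 1.8; for 30% or 70%, 7.5/7 = 1.1; for 80%, 5/7 = 0.7. Multi-category factors make it worse, so a joint model is not realistic.
- *Seven unadjusted tests at 0.05.* If independent, the chance of at least one false positive is 1 − 0.95⁷ = 0.30.

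These figures point to factor-by-factor estimates with intervals and no significance claims.

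**The case against.** Four objections deserve an answer.

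*The codebook may list tolerance.* It may, and tolerance is collected in any case. A reader might infer that the trial fails to capture tolerance; the documents do not support that. But 7b describes the codebook as a list of variables, and a list does not supply a method. What can be said is that tolerance is not named in 7a or 7b as printed.

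*Listing patient characteristics in 7b is a labelling slip.* Probably so. A reader might infer that section 7 models the factors as consequences of tolerance; nothing there does. But correcting the label alone still leaves no association analysis.

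*The tests in 7c were never meant for demographics.* This stands. Because demographics and characteristics are collected at both sessions, a reader might infer that the plan would test sex or education against itself a day or two later and produce a degenerate result. The test rules in 7c refer to assessment scores, and its descriptive sentences cover patient characteristics. Those variables do get a result; it is a summary, not a relation to tolerance.

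*It is a pilot and Aim 1 is not the primary outcome.* This limits the weight of the point. It does not remove it, since H1a is worded as a significance hypothesis under the first aim. A pilot can be exploratory and still state an analysis that matches its question.

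**Conclusion.** The point holds as a mismatch between hypothesis and analysis. H1a needs patient factors related to early tolerance; section 7 as printed names no tolerance outcome and states only pre/post tests, so none of the seven factors has a prespecified analysis against tolerance. Aim 1 receives descriptive summaries alone.

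It would go too far to conclude that the trial is unable to address Aim 1. The raw tolerance measure is recorded, and an analysis could be specified without new visits or procedures. The primary outcome is not affected. The point is worth correcting but does not threaten the trial as a whole.

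The conclusion rests on the printed text of sections 2, 4a and 7, and on the codebook being what 7b calls it. The precision figures depend on the assumptions shown and on all 25 early-arm patients providing data, so they are best cases.

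**What to change.** **In 7b**

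- Move patient characteristics out of the outcomes and describe them as baseline data from Session 1.
- Name OWSV tolerance at Session 1 as the Aim 1 outcome, measured by the duration already recorded under item E.2.ii.1 of section 4a.

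**In 7c**

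- Add an association analysis in the intervention arm: rank correlation of tolerance duration with each continuous factor, and difference in duration between categories for each categorical factor, each with a 95% confidence interval. Diagnosis, indication and comorbidity need sparse categories collapsed in advance.
- State beforehand how early-arm patients who are not trialled, or whose trial is deferred, are counted. One option is zero duration in the main analysis and exclusion in a sensitivity analysis. The choice matters, because zero duration mixes suitability for a trial with tolerance once trialled.
- Label the analysis exploratory and make no significance claims.

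**Check**

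Confirm against the codebook that education, indication and comorbidities are captured. Section 4a names demographic data and patient characteristics without itemising them.

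**Cost**

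A few lines of text, with no new visits; any factor missing from the codebook would have to be added. The limits should be stated openly: at most 25 patients, wide intervals, seven unadjusted comparisons, and an answer about tolerance (H1a) within one arm. That is narrower than the Aim 1 heading, which asks who would benefit.

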**Study Protocol**

Date: 2/06/18

Principal Investigator: [name]

Application Number: **IRB00080981**

- b. Study duration and number of study visits required of research participants.

The study duration is estimated to be 4 weeks per patient with a total of 3 visits by the study team.

- c. Blinding, including justification for blinding or not blinding the trial, if applicable.

Patients will not be blinded to intervention or control group.

- d. Justification of why participants will not receive routine care or will have current therapy stopped.

If patient is not willing to participate in the study, their routine care will not be altered. Participants in the control group will receive routine care, and participants in the intervention group will initiate the same intervention as routine care with timing to be 24-60 hours earlier than the current routine care.

- e. Justification for inclusion of a placebo or non-treatment group.

N/A

- f. Definition of treatment failure or participant removal criteria.

If there is a change in clinical condition that prevents study team from continuing with OWSV trial or if the patient is discharged from the hospital, the patient will be removed from the study.

- g. Description of what happens to participants receiving therapy when study ends or if a participant's participation in the study ends prematurely.

If participants receiving the OWSV complete the study (after Session 3), they will continue to use the OWSV per our current standard of care. If the participant's participation using the OWSV ends prematurely due to change in clinical condition, then they will be dropped from the study. But if their condition improves and warrants reuse of the OWSV, they will be offered the OWSV per our standards of care but will not be re-enrolled in the study.

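### The time-to-event secondary outcome has no usable method in section 7c: no between-arm test, and no way to keep patients who leave before the event

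*Combined protocol and SAP*

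**What the plan says.** Section 7b names "Time to events" as a secondary outcome, separately from length of stay and mortality. It does not say which events, from what origin, or until when. It refers to a codebook for further variables, which is not part of the documents.

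Section 7c gives the whole analysis plan:
- Description: "Mean, standard deviation, median and inter-quartile range will be calculated for continuous variables", with frequencies and percentages for categorical variables.
- Numeric test: "Paired t-tests will be used to compare pre and post assessment scores for continuous variables".
- Categorical test: "Chi square and Fisher Exact tests will be used to compare pre and post assessment scores of categorical variables".

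No survival method and no censoring rule appears anywhere.

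Observation can end before an event in several ways. Section 4b says "The study duration is estimated to be 4 weeks per patient". Under 4f, "if the patient is discharged from the hospital, the patient will be removed from the study", and so is a patient whose clinical condition prevents the valve trial from continuing. Section 7d drops patients whose condition prevents cuff deflation. Section 8b allows the valve trial to be deferred. Mortality is itself a listed outcome.

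**The concern.** Two gaps meet in this outcome. First, each patient has at most one time per event, so a pre/post paired test has nothing to pair, and 7c names no other test for a numeric variable. Second, some patients will leave observation without the event, and 7c does not say how they enter the summary.

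The easiest way to apply the continuous-variable rule is to average the times that exist. That selects patients on something that happens after randomisation. The slower arm loses more of its slow patients, so the two averages can look alike although one arm is reaching the event much faster.

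This matters because section 6a says that the trial studies when to start the valve, and section 9a offers participants the prospect of regaining speech sooner. Outcomes about speed are close to its purpose.

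**Working it through.** **The plan's own figure.** Section 7c counts "about 55 patients were awake and interactive while having a percutaneous tracheostomy tube at the hospital" and allows for 10% not interested: 55 × (1 − 0.10) = 49.5, rounded to 50. This reproduces the stated plan: "we will plan for a sample size of 50 with 25 in the intervention group and 25 in the control group". The number comes from availability. No alpha, power or effect is stated, so there is no power claim to check.

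**Inputs for the illustration.**
- From the documents: 25 per arm (7c), and about 4 weeks of observation (4b), taken as T = 28 days.
- Assumed, because the documents give none: exponential times, hazard ratio (HR) 2 or 3 favouring early use, control-arm proportion with the event by day 28 (p) from 30% to 90%, two-sided alpha 0.05, and no loss before day 28.

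**Mean among patients with the event.** The control rate is λ = −ln(1 − p)/T and the early-arm rate is HR × λ. The proportion with the event is P = 1 − exp(−rate × T). The mean time given the event is 1/rate − T × exp(−rate × T)/P.

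For p = 50% and HR 2:
- Control: λ = ln 2/28, so the median is 28 days. The mean given the event is 40.40 − 28 × 0.50/0.50 = 12.40 days.
- Early: the rate is 2λ, so the median is 14 days and P = 75%. The mean given the event is 20.20 − 28 × 0.25/0.75 = 10.86 days.

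A 14-day difference in medians becomes 12.40 − 10.86 = 1.5 days among patients with the event.

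**Power.** This was simulated with 4,000 trials per row. A Welch two-sample t-test on event-only times is compared with a log-rank test on all 50 patients censored at day 28. The mean differences come from the formula above.

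| HR 2: control / early with event | Event-only mean difference | Event-only t-test | Log-rank |
|---|---|---|---|
| 30% / 51% | 0.8 days | 6% | 33% |
| 50% / 75% | 1.5 days | 8% | 49% |
| 70% / 91% | 2.4 days | 15% | 59% |
| 90% / 99% | 3.3 days | 40% | 65% |

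At HR 3, for the same four control proportions, the event-only test has 7%, 18%, 44% and 83% power, against 74%, 90%, 94% and 96% for log-rank. With no true difference, both tests reject in about 5% to 6% of trials. In this set-up, then, the cost is lost sensitivity and not extra false positives.

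**What a log-rank test could achieve here.** By Schoenfeld's formula with equal arms, 80% power at HR 2 needs 4 × (1.96 + 0.84)²/(ln 2)² events, about 66. Freedman's formula gives 71. Both exceed the 50 patients planned.

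**The case against.** The strongest reply is that 7c is silent on this outcome and not mistaken about it. It limits paired t-tests to pre and post assessment scores, never classes times as ordinary continuous variables, and never says that event-free patients are left out. A median could also be reported properly if those patients were kept and ranked as longest, and 7c does not forbid that. This stands. A reader might infer that the plan prescribes an event-only analysis and is wrong as written. The documents do not support that, because exclusion is only what a plain summary of observed times would do.

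The power contrast also needs care. A reader might take it as the loss built into this plan. It is not: the two-sample t-test is a stand-in, and the event rates and hazard ratios are assumed. A reader might also conclude that an event-only comparison always leans towards no difference. The calculation shows this under constant hazards with censoring only at day 28. Early discharge, removal and death were not examined.

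There is a more basic gap too. The event, origin and end of observation are undefined. Section 4b's duration is an estimate, while 4g treats the study as complete after Session 3, which 4a ties to the first trach change. For an event such as first valve trial, the session windows (12-24 against 48-60 hours after tracheotomy) would largely fix the difference, and a test would mostly confirm the allocation. The unseen codebook might define events, but it is cited only as a list of variables.

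Finally, this is a secondary item in a pilot of 50, and no aim is framed as a time to event. That limits the priority. It does not supply a method.

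**Conclusion.** The point holds. As the plan stands, this outcome has no test that can be applied, no between-arm comparison, and no rule for keeping patients who leave before the event. Those three statements need no assumption.

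The harm from an event-only summary is conditional on that summary being used and on how many patients never reach the event. Under the stated assumptions at HR 2, power is 6% to 40% against 33% to 65% for log-rank. The gap narrows when nearly everyone has the event: at HR 3 with 90% of controls reaching it, 83% against 96%. Even the better method has limited power with 50 patients, so results should be read mainly as estimates. This is a cheap improvement worth making to a secondary outcome, and it does not undermine the trial as a whole.

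**What to change.** In section 7c, take this outcome out of the continuous-variable rule and state:
- each event by name, one common time origin for both arms (randomisation, or tracheotomy if justified), and a fixed end of observation;
- that all randomised patients are included, by assigned arm;
- Kaplan-Meier curves with a log-rank test, or cumulative incidence with death or discharge as a competing event where either prevents the event;
- as the main result, the proportion reaching the event by a fixed day in each arm, with a 95% confidence interval.

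Events whose timing is set by the visit schedule, such as first valve trial, should be described but not tested as outcomes.

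The cost is a few lines of text, slightly more programming, and a last-observed date for each patient. No extra patients or procedures are needed.

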#### **Specific Aim 2: Determine the effect of the early use of the OWSV on the quality of speech.**

Hypothesis 2a: The increase in the speech intelligibility scores from pre- to post- assessment will be significantly higher in the patients who receive early OWSV compared to those who receive it the traditional way 48 hours after undergoing a tracheostomy.

Research Question 2b: Is the duration of speech longer for patients who start using OWSV earlier compared to those who start late?

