#### **Specific Aim 3: Determine the effect of early use of the OWSV on clinical outcomes.**

Hypothesis 3a: The increase in the health-related quality of life scores from pre- to post- assessment will be significantly higher in the patients who receive early OWSV compared to those who receive it the traditional way 48 hours after undergoing a tracheostomy.

Hypothesis 3b: There will be no significant changes in the rate of complications between patients receiving early versus standard use of the OWSV.

Hypothesis 3c: Patients who begin to use the OWSV early will have a significantly shorter lengths of stay in the ICU than patients who start using OWSV after 48 hours.

**3. Background** (briefly describe pre-clinical and clinical data, current experience with procedures, drug or device, and any other relevant information to justify the research)

Current standard of care to wait 48 hours following tracheostomy procedure to initiate OWSV assessment and treatment, however, there is scant evidence in the literature justifying this amount of time. 201 patients out 272 patients who received a tracheostomy received SLP consult for in 2014. Based on prior data from the tracheostomy database 30% of mechanically ventilated and / or tracheotomized patients tend to be awake and interactive, and attempt to communicate.

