**Sequence and timing:**

- A. Screening by Tracheostomy Nurse Practitioner following percutaneous tracheotomy
1. Glasgow Coma Scale (GCS)
  2. Richmond Agitation Sedation Scale (RASS)
- B. Speech-Language Pathologist consult is placed for patients meeting study inclusion criteria
- C. Patient consent is obtained by Tracheostomy Nurse Practitioner or Speech-Language Pathologist
- D. Randomization into Intervention and Control groups
- E. Session 1 within 12-24 hours following percutaneous tracheotomy:
1. Both groups complete pre-assessment consisting of the following:
    - i. Electronic Patient Records (POE, EPR, or EPIC)
      1. Demographic Data
      2. Patient Characteristics
      3. Sequential Organ Failure Assessment (SOFA)
    - ii. Confusion Assessment Method for the ICU (CAM-ICU)
    - iii. Health-related quality of life survey, Quality of Life – Mechanical Ventilation (QOL-MV)
    - iv. Tracheostomy-related assessment
      1. Trach size
      2. Mechanical ventilation status
      3. Secretions & tolerance of cuff deflation
      4. Presence of complications
        - i. Bleeding at stoma
        - ii. Subcutaneous air
        - iii. Infection at stomal site
        - iv. Pneumothorax
        - v. Accidental decannulation
  2. Intervention Group completes standard SLP evaluation and OWSV trial:
    - i. SLP evaluation includes the following to assess candidacy for OWSV trial:
      1. Level of alertness
      2. Cranial nerve exam
      3. Ability to cough
      4. Ability to tolerate cuff deflation
      5. Ability to tolerate finger occlusion
      6. Vocal quality
    - ii. If appropriate, OWSV will be trialed and assessed for the following:
      1. Duration of tolerance
      2. Change in vital signs
      3. Vocal quality
      4. Presence of air trapping
      5. Sentence Intelligibility Test
    - iii. Recommendations are made for OWSV use outside of SLP supervision
      1. Supervision requirement (RN, Respiratory therapist, trained family, independent)
      2. Duration of OWSV use
  3. Control Group receives no further evaluation or treatment during Session 1, which constitutes current standard of care.
- F. Session 2 within 48-60 hours following percutaneous tracheotomy:
1. Both groups complete post-assessment:

Date: 2/06/18

Principal Investigator: [name]

Application Number: IRB00080981

[figure not shown]
- i. Electronic Patient Records (POE, EPR, or EPIC)
    1. Demographic Data
    2. Patient Characteristics

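### Section 7c tests only change from pre to post and names no comparison of the randomised arms, so hypotheses 2a, 3a, 3b and 3c have no planned test

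*Combined protocol and SAP*

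**What the plan says.** Section 7c gives descriptive summaries and then two inferential procedures. For continuous outcomes: "Paired t-tests will be used to compare pre and post assessment scores for continuous variables". For categorical outcomes: "Chi square and Fisher Exact tests will be used to compare pre and post assessment scores of categorical variables". The codebook is cited in section 7b only as a list of further variables. No other section names a test, model or estimate that compares the arms.

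The hypotheses in section 2 are between-arm statements:

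- 2a, on the primary outcome: "The increase in the speech intelligibility scores from pre- to post- assessment will be significantly higher in the patients who receive early OWSV", against 48-hour use.
- 3a makes the same kind of claim for quality of life: "The increase in the health-related quality of life scores from pre- to post- assessment will be significantly higher".
- 3b: "There will be no significant changes in the rate of complications between patients receiving early versus standard use of the OWSV".
- 3c: "Patients who begin to use the OWSV early will have a significantly shorter lengths of stay in the ICU than patients" starting after 48 hours.

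Section 4 (Sequence and timing) places the Sentence Intelligibility Test (SIT) within the intervention arm's Session 1 valve trial, under the line "If appropriate, OWSV will be trialed and assessed for the following". For the other arm at that session: "Control Group receives no further evaluation or treatment during Session 1, which constitutes current standard of care".

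**The concern.** Patients are randomised so that early and standard timing can be compared, but the tests named in 7c compare each patient with himself or herself. These are different questions. A patient seen first at 12-24 hours and again at 48-60 hours after tracheotomy may improve for reasons unrelated to the valve, and a paired test counts all of that as change.

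If the plan is followed literally, the trial reports change over time and gives no test or estimate of the timing effect. A significant paired result in the early arm could be recovery alone. Significant results in both arms would not show whether early use is better.

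**Working it through.** **The plan's own figure.** The sample size is accrual arithmetic: 55 × (1 − 0.10) = 49.5, rounded to 50, or 25 per arm. Section 7c gives no alpha, power, effect size or SD. I assume two-sided 0.05 below and show a range of effects.

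**Named tests against hypotheses.**

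| Hypothesis | Contrast needed | What 7c provides |
|---|---|---|
| 2a, SIT | Early v control, difference in increase | Paired t-test; no control pre score is scheduled |
| 3a, QOL-MV | Early v control, difference in increase | Paired t-test of pre v post only |
| 3b, complications | Early v control rates | Chi-square/Fisher of pre v post |
| 3c, ICU stay | Early v control | Nothing: no pre value exists |

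Mortality, a listed secondary outcome, has no pre value either.

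**Primary outcome.** SIT is absent from the pre-assessment common to both arms. It is listed only within the Session 1 valve trial, which controls do not have. A paired SIT test is therefore possible in the early arm at most, and 2a's difference in increases cannot be computed. The early arm's Session 1 score is itself taken during the valve trial, so it is not a pre-treatment baseline.

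**Paired tests within arms, no true arm difference.** This applies to outcomes measured twice in both arms, such as QOL-MV, and not to SIT. Both arms gain d SD of the within-patient change. Power p is from the noncentral t with 24 df and noncentrality d√25. With independent arms, the chance that early is significant and control is not is p(1 − p).

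| d | p | p(1 − p) |
|---|---|---|
| 0 | 0.050 | 0.048 |
| 0.2 | 0.161 | 0.135 |
| 0.4 | 0.484 | 0.250 |
| 0.6 | 0.821 | 0.147 |
| 0.8 | 0.970 | 0.029 |
| 1.0 | 0.998 | 0.002 |

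A simulation of 100,000 trials at d = 0.4 gave 25.1% for early-only significance, against 4.9% for a two-sample t-test on change. If the paired test instead pooled all 50 patients, it would reject in 79% of trials at d = 0.4 with no arm difference.

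**Paired tests within arms, early truly better.**

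- Gains 0.8 v 0.4 SD: both paired tests significant in 0.970 × 0.484 = 47% of trials; two-sample power for a 0.4 SD difference is 28%.
- Gains 1.6 v 0.8 SD: both significant in about 1.000 × 0.970 = 97%; two-sample power for a 0.8 SD difference is 79%.

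When both paired tests are significant, they show no contrast between the arms.

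**Paired categories.** Chi-square and Fisher treat pre and post as independent samples. Take 2/25 pre and 8/25 post (illustrative counts). Fisher gives p = 0.074. Exact McNemar gives 0.031, 0.070 or 0.109 for discordant pairs of 6 v 0, 7 v 1 or 8 v 2. The error can go either way.

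**Hypothesis 3b.** With 25 per arm, 5 v 0 complications gives Fisher p = 0.0502. With 0 v 0, the Newcombe 95% interval for the risk difference still runs from −13 to +13 percentage points. A non-significant result does not show equal safety.

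**The case against.** The strongest defence is that 7c is loosely worded. Section 2 states the contrast, comparator and direction for each hypothesis, chi-square and Fisher are ordinary two-group tests, and this is a pilot whose size was set by accrual, so by-arm description might suffice. It is true that section 2 poses the between-arm question. But 7c says what each test compares, and a paired t-test cannot compare independent arms. The pilot label may excuse the absence of a power calculation, but 2a, 3a and 3c are worded as significance claims.

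A second objection is that the missing control SIT is inferred from its place in a list. The instrument table does not restrict SIT to one arm, 2a presupposes a pre score in both, and the Session 2 list does not itemise SIT at all. This is fair as a description of an inconsistency: 2a needs a control baseline that the session schedule does not supply. The inconsistency still has to be resolved before 2a can be analysed.

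Third, the size of the problem rests on assumed gains and on a way of reading two paired tests that the plan does not state; 7c does not even say whether they are run by arm or pooled. That stands. The figures illustrate the risk and do not predict this trial's results.

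**Conclusion.** The concern holds and must be fixed before analysis. That 7c names no between-arm test, and that 2a, 3a, 3b and 3c all require one, follows from the text and needs no assumption. The gap includes the primary outcome, for which the schedule also gives controls no pre score.

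The percentages assume normally distributed changes, independent arms, 25 analysed per arm and two-sided 0.05. Over equal gains of 0.2 to 0.8 SD, the early-arm paired test is significant in 16% to 97% of trials with no timing effect. Early-only significance peaks at 25%.

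The right test will still be imprecise. A two-sample t-test on 25 v 25 has 80% power only for a difference of about 0.81 SD, and 41% power at 0.5 SD. Intervals will therefore say more than p-values.

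**What to change.** Rewrite 7c so that comparisons by randomised arm, each with a 95% confidence interval, are the hypothesis tests.

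- **Speech intelligibility (2a):** compare Session 2 SIT between arms. State that SIT is part of the Session 2 valve trial in both arms, and restate 2a as a Session 2 difference. SIT exists only for patients who were given a valve trial and not dropped, so report by arm how many have no score and why. That reporting exposes the selection but does not remove it.
- **QOL-MV (3a):** compare change between arms or, more efficiently, use ANCOVA of the Session 2 score adjusted for Session 1. With equal variances at both sessions and correlation ρ, the ANCOVA variance relative to change scores is (1 + ρ)/2, or 0.65, 0.75 and 0.85 for assumed ρ of 0.3, 0.5 and 0.7.
- **Complications (3b) and mortality:** Fisher exact between arms with the risk difference and its interval. State that non-significance will not be read as equal safety.
- **ICU length of stay (3c):** a between-arm rank or time-to-discharge comparison that accounts for death.
- **Pre/post summaries:** keep as descriptive, with McNemar for paired categories.

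Research question 2b also compares the groups and has no named method; it can be covered in the same edit.

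The cost is rewording 7c and hypothesis 2a, plus a matching line in the Session 2 list in section 4. Both arms already have a valve trial at Session 2, so no extra patients or visits are needed. Section 8d says analysis starts only after data collection and de-identification, which leaves room for a dated change before then.
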